9. ADHERENCE TO PROTOCOL/AMENDMENT(S)

The Investigator will be required to adhere to the final protocol. Any changes to the protocol, except those necessary to eliminate apparent hazards, will require prior approval by the local reviewers through the submission of a protocol amendment. In the event of emergency, the Investigator shall engage any medical procedures that he/she deems appropriate. However, all such procedures must be promptly reported to the PI and Ethical Committee.

The Ethical Committee which granted approval for the study must be notified of all changes in the protocol and must provide written approval if changes are substantial (e.g. increase the risk to the subject, and/or affect the rights of the subject or validity of the investigation, change of/within study population, number of participants or changes of patients' age group).

Departures from eligibility requirements may be allowed on a case-by-case basis by the medical monitor or other authorized sponsor representative. Such departures must be medically and scientifically justified, must be pre-authorized, and must be documented in the CRF and tracked as official eligibility waivers.

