2. TREATMENTS

Plus Powder and Biofilm Discloser[®] by EMS Electrical Medical Systems SA, CH 1260-Nyon, Switzerland will be delivered to the study center prior study start.

Concomitant Therapy

A necessary concomitant medication or therapy is permitted as long as it is not excluded in the exclusion criteria. Every medication has to be reported in the CRF (Appendix 1) and in the Concomitant Medication form (Appendix 2). All changes during the study are to be reported in the CRF. Usage of prohibited therapy will lead to the exclusion of the subject.

Blinding and Randomization

Blinding: The statistician will be blinded to the 4 groups identification, and defined as all the possible combination of A-b (treatment) and B-b (DPA usage).

Randomization and allocation concealment: The randomization will be done based on a computer-generated table, using a random blocks randomization algorithm, that links each patient to one of the four treatment combinations

Implementation: The Principal Investigator will be informed immediately of Serious Adverse Events (SAEs), regardless of the causality relationship between the administration of the investigational treatment and the SAE.

3. **PROCEDURE**

Screening and Selection of Subjects

Patients visiting the Department of Dentistry at Brescia University will be asked to participate in this study. Subjects will report to the clinical facility and be screened by the dental examiner to identify those subjects who meet the inclusion/exclusion characteristics. The findings of this initial screening procedure will be recorded on the CRF. Subjects who meet the inclusion/exclusion characteristics and sign an Informed Consent Form will be entered into the study.

Baseline Oral Soft and Hard Tissue Assessment

All subjects will receive an evaluation of their oral soft and hard tissues. This examination will include an evaluation of the soft and hard palate, gingival mucosa, buccal mucosa, mucogingival fold areas, tongue, sublingual and submandibular areas and the tonsillar and pharyngeal areas. The results of this evaluation will be recorded on the CRF.

Clinical Periodontal Evaluation

All patients receiving treatment will be evaluated by the dental examiner for the following assessments

- Full Mouth Plaque Score (FMPS).

All parameters will be recorded in the CRF.

Treatment

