5. MONITORING AND AUDIT

Study Monitoring

The study will be monitored by the Principal Investigator at periodic intervals during the course of the study to ensure that the study is being conducted according to Good Clinical Practice.

The Investigators will be contacted by the PI on a regular basis. On this occasion, the progress of the study will be discussed with the Investigator and the CRFs will be checked for completeness and consistency and to verify compliance with the study protocol.

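### Section 9 allows case-by-case eligibility waivers with no criterion off limits and no stated Ethical Committee step, and this is not reconciled with the plan's adherence, approval, entry and prohibited-therapy rules

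*Combined protocol and SAP*

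**What the plan says.** All references are to the combined protocol and SAP.

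- **Section 9, last paragraph, the waiver.** "Departures from eligibility requirements may be allowed on a case-by-case basis by the medical monitor or other authorized sponsor representative". The next sentence sets the conditions: "Such departures must be medically and scientifically justified, must be pre-authorized, and must be documented in the CRF and tracked as official eligibility waivers".
- **Section 9, first paragraph.** "The Investigator will be required to adhere to the final protocol". On amendments: "Any changes to the protocol, except those necessary to eliminate apparent hazards, will require prior approval by the local reviewers".
- **Section 9, second paragraph.** The Ethical Committee "must be notified of all changes in the protocol and must provide written approval if changes are substantial". The examples of a substantial change include greater risk to the subject and "change of/within study population, number of participants or changes of patients' age group".
- **Section 3, Screening and Selection of Subjects.** "Subjects who meet the inclusion/exclusion characteristics and sign an Informed Consent Form will be entered into the study". No waiver route is mentioned.
- **Section 2, Concomitant Therapy.** Other therapy is allowed unless the exclusion criteria rule it out, and a subject who uses prohibited therapy is to be excluded.
- **Study Population.** The exclusions include a history of erythritol allergy, current radiotherapy or chemotherapy, oral tumours and orthodontic appliances. The inclusion criteria set the age range (6 to 12 years) and the minimum dentition. None is marked as exempt from waiver. Major protocol deviators who are excluded from the analysis are replaced.
- **Section 5.** "The study will be monitored by the Principal Investigator at periodic intervals".

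**The concern.** Eligibility criteria do two jobs here. Some protect the child (allergy, cancer treatment, oral pathology). Others define the mouths in which residual plaque area (RPA) is measured (appliances, tooth counts). The waiver paragraph covers both kinds without distinction and without a cap on numbers. The participants are children having one session of professional oral hygiene, and nothing described in the plan makes it necessary to enrol a particular child who does not qualify.

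Two things are at stake. The first is safety: a child whom the exclusions were written to keep out could be entered with no Committee involvement stated. The second is what the result describes: waivers of the appliance or dentition criteria admit children whose tooth surfaces differ from those of the stated population. A related gap is that the plan does not say whether a child entered by waiver counts as a major deviator, to be dropped and replaced, or stays in the analysis.

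**Working it through.** The plan states no figure for waivers, so this is mainly a comparison of texts, with one small calculation.

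1. **Reach of the waiver.** The paragraph speaks of eligibility requirements in general. The four conditions that follow (justification, prior authorisation, entry in the CRF, tracking) govern how a waiver is granted. They do not limit which criterion may be waived or how often. The wording therefore reaches every item in the Study Population lists, including the allergy and cancer-treatment exclusions. This follows from the absence of an exemption; the text does not name those criteria as waivable.

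2. **Who grants it.** A medical monitor is mentioned nowhere else in the body text. The Responsibilities section gives duties only to the principal investigator and the statistician. The monitoring in section 5 is done by the principal investigator, and the sponsor is the hospital at which this single-centre trial is run. The role that decides on waivers is thus not described.

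3. **Against the rest of section 9.** The investigator must follow the final protocol. The only stated exception to prior approval of changes is the removal of apparent hazards, and waivers are not listed as another. The approval rule concerns changes to the protocol, whereas a waiver concerns one child. Even so, a waiver can raise the risk to a subject or alter who is in the study population, which are effects the section itself treats as substantial. The section does not say how the two rules fit together.

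4. **Against section 3.** Subjects who meet the criteria and consent are entered. The plain sense is that those who do not meet them are not entered, although the sentence does not say *only*.

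5. **Against section 2.** Permitted therapy is tied to the exclusion criteria, and prohibited therapy leads to exclusion of the subject. A child entered under a waiver for current chemotherapy would, on the natural reading, have to be excluded at once. The two rules cannot both operate for that child.

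6. **Exposure of an allergic child.** Inputs: four arms of 30, N = 120 (section 4, Sample size determination). Section 1 uses erythritol powder in the two GBT arms; the two US+C arms are described with a piezoceramic device, rubber cup and polish. Chance of allocation to an erythritol arm = (30 + 30) / 120 = 0.50. This assumes that the arms are equal in size.

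7. **Weight of one waiver.** One child is 1/30 = 3.3% of an arm. No total can be given, because the plan states no expected number of waivers.

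8. **Effect on the comparison.** A waiver must be authorised in advance, and section 1 places screening and entry before randomisation at T0. A waived child should therefore be allocated by the same random process as any other. Nothing in the plan shows that waivers would fall unequally on the arms.

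**The case against.** The strongest defence is that the paragraph is a controlled procedure. It carries four conditions, one of which is medical justification, and that would stand in the way of waiving an allergy exclusion lightly. It is also part of the protocol that the Ethical Committee reviews before the study starts (section 11), so the Committee would have approved the waiver route in advance. This has force. A reader might infer an unconditional power or a literal contradiction of the ethics-approval rule, and the documents support neither. They support an unreconciled conflict, because the conditions exempt no criterion, describe no authorising role and leave the Committee out of the individual decision.

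Other tempting readings also go too far:

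- *That section 3 forbids any other entry.* It describes the ordinary route and is silent on waivers.
- *That nobody exists to grant a waiver.* Signature and contact pages were removed from the text, and section 10 treats the principal investigator and the sponsor as distinct. Only the lack of a described role can be noted.
- *That a waived allergic child would certainly receive erythritol.* That depends on the randomisation.
- *That waivers would bias the treatment comparison, or that the trial would cease to describe its population.* Entry precedes randomisation, and the number of waivers is unknown.

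It can also be said that a total ban is one choice among several, since safety criteria could be exempted or the Committee notified. That is fair, but either narrower repair would leave the fit with section 3 and the analysis of waived children still to be settled.

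**Conclusion.** The concern holds as a conflict between stated rules. Section 9 permits eligibility waivers that reach every criterion, with no stated Committee step and with an authorising role that is not described. This is not reconciled with the adherence and approval rules in the same section, the entry rule in section 3 or the prohibited-therapy rule in section 2. The procedural conditions on waivers are real and reduce the risk without removing it.

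The quantifiable size is modest: about a 1 in 2 chance of an erythritol arm for an allergic child, if one were entered and arms are equal, and 3.3% of an arm per waived child. The overall effect cannot be sized without a number of waivers. No effect on the between-arm test is demonstrated. The change should still be made, because it protects children in a single-session trial, keeps the stated population intact and costs little.

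**What to change.** Delete the last paragraph of section 9 and state in its place that:

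- no eligibility waivers are granted;
- a child who does not meet all criteria is not randomised;
- a criterion that proves unsuitable is changed only by an amendment approved by the Ethical Committee.

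Add a rule for children found ineligible only after randomisation. They are recorded as protocol deviations and kept in the primary analysis in the arm to which they were randomised, where RPA is available. The exclude-and-replace rule in Study Population should be amended to say that it does not apply to them. Without this step, a ban on waivers could simply move the problem into post-randomisation exclusions. This rule concerns the analysis only; how such a child is managed clinically is a separate matter.

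If the sponsor prefers to keep some form of waiver, the passages must at least be reconciled: which criteria it reaches, who grants it, what part the Committee plays, and how waived children are analysed.

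The cost is one amendment to a short passage, the loss of case-by-case flexibility, and possibly a few lost enrolments over the 36-month recruitment period.

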10. ADMINISTRATIVE ASPECTS

Final Report

Following the completion of the study, the PI shall prepare a final study report. The final report will include a general description of the conduct of the study including protocol deviations, subject withdrawals, discussion of any adverse events, safety and efficacy data, and statistical analysis of the data. This report will be shared with the Co-investigator at the Participating Centre by the Principal Investigator, and agreed upon parts before being sent to the Sponsor.

Data Retention

The information in this and any further document contains trade secrets and commercial information that are privileged or confidential and may not be disclosed unless such disclosure is required by law or regulations.

In any event, persons to whom the information is disclosed must be informed that the information is privileged or confidential and may not be further disclosed by them.

The files pertaining to this study will be kept by the University-Hospital of Brescia for a period of 15 years from the day of delivery of the final report and will be available for consultation by competent authorities at any time.

The Investigators will retain originals of the approved study protocol, copies of completed CRFs, subjects' participation agreements, relevant source documents and all other supporting documentation related to the study for a period of 5 years. These files must be made available for inspection upon reasonable request by an authorized representative of EMS or the competent authorities.

11. ETHICAL ASPECTS AND REGULATIONS

Ethical Conduct of the Study

This study is to be conducted in accordance with the ethical principles of the Declaration of Helsinki and according to local laws and regulations.

Independent Ethics Committee (IEC) and Relevant Authorities

Before starting the study, the study protocol will be subject to review by the Ethical Committee of the University-Hospital of Brescia. As required by law, the study will be notified to authorities if applicable. No subject should be admitted to the study before the Ethical Committees issue their written favourable opinion of the study. Periodic status reports must be reported to the ethics committee at least annually as well as notification of the completion of the study. The investigator

must maintain an accurate and complete record of all reports and documents submitted to and received from the ethics committee according to the ISO 14155:2011 Clinical Investigation of Medical devices for human subjects.

Subject information and Informed consent form

The purpose and description of the study in lay language, possible adverse reactions, risks and benefits of participation and the subject's right to withdraw without prejudice at any time must be explained to each subject. Each subject must read, understand and sign the informed consent form provided before any study-related procedure.

Subject data protection and Confidentiality

The name of the subject as well as all other personal data will be kept strictly confidential by the Investigator. If due to medical reasons, it is necessary to identify the subject during the study course, this will be done under medical secrecy.

The subject has given his/her consent before the beginning of the study. In case of withdrawal of this consent subject has to leave the study.

All subjects will agree to verify, by letter, that they participated in this study, if called upon to do so.

New Findings

Subjects will be informed of any significant new findings related to study products or procedures when they become known during the course of this clinical research study. Such information may affect the subject's decision to continue participation in the study.
